### **3.1.2 Dose-Escalation Phase**

The purpose of the dose-escalation phase is to identify the RP2Ds and regimen for idasanutlin and venetoclax when combined with a fixed dose of obinutuzumab in patients with R/R FL and the RP2D for idasanutlin and venetoclax when combined with 375 mg/m^2 of rituximab in patients with R/R DLBCL. The RP2Ds will be based on the MTDs of idasanutlin and venetoclax when combined with a fixed dose of obinutuzumab or with 375 mg/m^2 of rituximab, but will also take into account all safety data during treatment. There could be two different RP2Ds and/or regimens dependent on the combination of idasanutlin, venetoclax plus obinutuzumab or idasanutlin, and venetoclax plus rituximab.

A minimum of 9 patients and a maximum of 60 patients will be enrolled during the dose-escalation phase. Cohorts of 3–6 patients each will be treated at escalating doses of idasanutlin and venetoclax in accordance with the treatment regimens and dose-escalation rules described in Section [3.1.2.2](#).

A Bayesian mCRM (see Section [3.1.2.3](#)) is planned to guide the dose-escalation phase to determine the MTD that achieves the efficacious exposure observed. The principle underlying this trial design is the assessment of the dose-toxicity relationship in a safe and efficient manner, allowing for enrollment of patients at subsequent dose levels and/or defining the MTD with robust data, including data for patients from Study BH29812 (obinutuzumab or rituximab in combination with idasanutlin), when available.

Patients will be closely monitored for adverse events during the DLT assessment window, defined as the first two treatment cycles. Adverse events meeting the criteria for

DLT, as defined in Section 3.1.2.1, will be reported to the Sponsor within 24 hours (see Section 5.4.2).

Patients experiencing a DLT during the DLT window (first two cycles of treatment) will permanently discontinue study treatment.

Patients who discontinue from the study prior to completing the DLT assessment window for reasons other than a DLT will be considered non-evaluable for dose-escalation decisions and MTD assessments and will be replaced by an additional patient at that same dose level. Patients who miss more than one dose of obinutuzumab or rituximab, idasanutlin, or venetoclax during the DLT assessment window for reasons other than a DLT will also be considered non-evaluable and will be replaced.

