### 3.1.2.1 Definition of Dose-Limiting Toxicity

In this study, a DLT is defined as at least one of the following events occurring during the first two cycles of treatment and assessed by the investigator as clearly not related to the patient's underlying disease:

- Any Grade 5 adverse event unless unequivocally due to the underlying malignancy or extraneous causes
- Adverse event of any grade that leads to a delay of more than 14 days in the start of the next treatment cycle
- Hematologic adverse events that meet any of the following criteria:
  - Grade 3 or 4 neutropenia in the presence of sustained fever of  $>38^{\circ}\text{C}$  (lasting for  $>5$  days) or a documented infection
  - Grade 4 neutropenia lasting for  $>7$  days *despite adequate supportive care measures. G-CSF may be used to treat Grade  $\geq 3$  neutropenia but should not be used as prophylaxis in the DLT period.*
  - Grade 3 or 4 thrombocytopenia if associated with grade  $\geq 3$  bleeding
  - Grade 4 thrombocytopenia lasting for  $>7$  days
- Grade 3 or 4 non-hematologic adverse event, with the following exceptions:
  - Grade 3 or 4 IRRs
    - Note that IRRs are not dose-dependent events. They may occur even after a small amount of drug has been administered.
  - Grade 3 laboratory TLS without manifestations of clinical TLS (see [Appendix 5](#) for the Howard-based criteria for clinical and laboratory TLS)
  - Grade 3 AST or ALT increase lasting  $<7$  days
  - Grade 3 diarrhea that responds to adequate therapy within 48 hours

- Grade 3 nausea or vomiting that occurs in the absence of premedication and responds to adequate therapy within 72 hours
- Grade  $\leq 3$  fatigue, asthenia, anorexia, or constipation that resolves to Grade  $\leq 2$  in  $\leq 7$  days
- Any increase in hepatic transaminase  $> 3 \times$  baseline AND an increase in direct bilirubin  $> 2 \times$  ULN, WITHOUT any findings of cholestasis or jaundice or signs of hepatic dysfunction AND in the absence of other contributory factors (e.g., worsening of metastatic disease or concomitant exposure to known hepatotoxic agent or of a documented infectious etiology) is suggestive of potential drug induced liver injury (DILI) (according to Hy's Law) and will be considered a DLT.

Other toxicities that are considered clinically relevant and related to study treatment as determined by the investigator and the Medical Monitor may also be considered DLTs.

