#### **4.6.2 Study Treatment Discontinuation**

Study treatment should be permanently discontinued in patients who experience any of the following:

- A DLT during the DLT window in patients enrolled in the dose-escalation phase
- Anaphylaxis, acute respiratory distress, or Grade 4 IRR
  - If a Grade 3 IRR is recurrent during the second and subsequent cycles, study treatment may be discontinued at the discretion of the investigator, following an individual benefit–risk assessment.
- Any adverse event that leads to a delay of more than 21 days in the start of the next treatment cycle

- Any hematologic adverse event that meets criteria for permanent discontinuation according to the guidelines provided in Section 5.1.8
- Hy's Law cases
- Grade  $\geq 3$  non-hematologic adverse event that has a reasonable possibility of being related to study treatment and either is life threatening or does not resolve to Grade  $< 2$  within 21 days
- Disease progression
- Pregnancy

In case of toxicity solely attributable to one drug of the combination requiring discontinuation, the other study drugs may be continued for patients experiencing clinical benefit as determined by the investigator after discussion with the Medical Monitor.

The primary reason for study treatment discontinuation should be documented on the appropriate eCRF.

Patients who discontinue study treatment will not be replaced, except as outlined below:

- During the dose-escalation phase, patients who discontinue study treatment prior to completing the DLT assessment window for reasons other than a DLT will be replaced by an additional patient at that same dose level.
- Patients who discontinue before having received at least one dose of each component of the combination will be replaced.

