Grade 3 or 4 hematologic toxicity a, b	
For patients who have had one or no prior dose reductions:
 
 
• Withhold study treatment.a
 
• Administer RBCs or platelets as required.
 
• If patient has not already initiated G-CSF, initiate prophylactic G-CSF for current and subsequent cycles.
 
• If improvement to Grade <math>\leq 2</math> or baseline within <math>\leq 14</math> days after the scheduled date for the next cycle, resume obinutuzumab or rituximab at full dose and resume idasanutlin and venetoclax at current dose.
 
• If improvement to Grade <math>\leq 2</math> or baseline 15–21 days after the scheduled date for the next cycle, resume obinutuzumab or rituximab at the full dose and resume the last escalated drug(s) at a reduced dose according to guidelines in Section 5.1.8.1 for current and subsequent cycles.
 
 
No more than three dose reductions of idasanutlin or venetoclax are allowed.
 
 
• If study treatment is withheld for <math>>21</math> days, permanently discontinue study treatment.
 
• Permanently discontinue study treatment if any of the following events occur: 
 
– Grade 3 or 4 thrombocytopenia of any duration if associated with Grade <math>\geq 3</math> bleeding
 
– Recurrent Grade 3 or 4 neutropenia if associated with fever of <math>>38^{\circ}\text{C}</math> for <math>>5</math> days) or a documented infection despite use of G-CSF and after one idasanutlin dose reduction and/or one venetoclax dose reduction or reduced schedule
 
– Recurrent Grade 4 neutropenia or thrombocytopenia lasting more than 7 days despite use of G-CSF (for neutropenia) and after one idasanutlin dose reduction and/or one venetoclax dose reduction/reduced schedule
 
 
 
 
For patients who present with recurrent Grade 3 thrombocytopenia/neutropenia in consecutive cycles:
 
If despite the use of G-CSF, for subsequent cycles, modify the venetoclax dose by reducing to next dose level or decrease the dosing schedule; reduce idasanutlin to the next dose level (see guidelines in Section 5.1.8.1).
 
For patients who have had reductions in three doses (either as single drug dose reduction or double drug reduction in the same time) or for patients who reach the lowest dose level and no further dose reduction is applicable (see Section 5.1.8):
 
 
• Permanently discontinue study treatment.
 

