**Table 18 Guidelines for Management of Non-Hematologic Toxicities**

Event	Action to Be Taken
General guidance for treatment delays, discontinuation, and resumption	
 
• If study treatment is withheld for > 21 days because of a toxicity that is attributable to study treatment, permanently discontinue study treatment.
 
• Permanently discontinue study treatment for Grade 4 events.
 
• When a treatment cycle is delayed because of toxicity resulting from any component of the regimen, all study treatment should be held and resumed together to remain synchronized.
 
• Dosing may be resumed after resolution to Grade <math>\leq 1</math> or baseline status. Resumption of dosing without complete resolution of toxicity may be considered in special circumstances after having obtained Medical Monitor agreement.
 

IRRs and anaphylaxis	
 
• Guidelines for the management of IRRs are provided in Section 5.1.1.1. In case of Grade 4 IRRs or anaphylaxis, study treatment should be permanently discontinued.
 

Clinical and laboratory TLS	
Grade 4 events:
 
 
• Permanently discontinue study treatment in the case of Grade 4 events.
 
 
Grade <math>\leq 3</math> events:
 
 
• Withhold study treatment. a
 
• Correct electrolyte abnormalities, monitor renal function and fluid balance, and administer supportive care, including dialysis as indicated.
 
• If symptoms (laboratory and clinical) have resolved completely, resume obinutuzumab or rituximab at full dose and resume venetoclax and idasanutlin at current dose.
 

New-onset neurologic manifestations suggestive of PML	
 
• Withhold study treatment. a
 
• Consult with a neurologist if PML is suspected (refer to Section 5.1.1.5 for guidance on investigations).
 
• If PML is ruled out, resume obinutuzumab or rituximab at the full dose and resume idasanutlin and venetoclax at the current dose.
 
• If PML is confirmed, permanently discontinue study treatment.
 

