**Table 18 Guidelines for Management of Non-Hematologic Toxicities (cont.)**

Event	Action to Be Taken
Diarrhea (cont.)	
Grade 2 or 3 diarrhea:
 
 
• If Grade 3 diarrhea occurs between Days 1 and 5 of the treatment cycle, withhold study treatment only if diarrhea does not improve to Grade <math>\leq 2</math> within 48 hours with appropriate treatment. After the study treatment is withheld, if diarrhea improves to Grade <math>\leq 2</math>, resume obinutuzumab or rituximab at the full dose and resume idasanutlin and venetoclax at a reduced dose according to guidelines in Sections 5.1.8.1 and 5.1.8.2 for current and subsequent cycles.
 
• If Grade 3 diarrhea is present at the time of the next planned cycle, withhold study treatment. If diarrhea improves to Grade <math>\leq 2</math>, resume obinutuzumab or rituximab at full dose and resume idasanutlin and venetoclax at a reduced dose according to guidelines in Sections 5.1.8.1 and 5.1.8.2 for current and subsequent cycles.
 
 
Management for diarrhea:
 
 
• Rule out other or concomitant causes, including, but not limited to, medications, Clostridium difficile infection, malabsorption/lactose intolerance, fecal impaction, and dietary supplements high in fiber.
 
• Initiate treatment at the time of onset.
 
• Administer loperamide 4 mg as loading dose; and up to 2 mg every 4 hours or after every unformed stool (for a maximum daily dose of 16 mg), or per institutional standard.
 
• For subsequent episodes, use 4 mg QD prophylactic loperamide 30 minutes before subsequent dosing. If diarrhea persists after 48 hours despite administration of the maximum recommended daily loperamide dose (16 mg/24 hr), second-line agents may be considered (diphenoxylate, atropine, octreotide, budesonide, or tincture of opium). Encourage patients to hydrate abundantly and self-medicate with loperamide 2 mg in the event that diarrhea recurs (up to 2 mg every 4 hours or after every unformed stool for a maximum daily dose of 16 mg), or per institutional standard.
 
• Monitor electrolyte levels closely and correct as appropriate.
 
• Administer IV fluids as clinically indicated.
 
• Upon presentation of Grade 3 diarrhea or diarrhea persists for >24 hours despite maximum recommended daily loperamide dose, exclude presence of active infections (e.g., C difficile). If present, treat infection(s), according to local guidelines.
 

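### In Cycles 1 and 2 of dose escalation, Tables 16 to 18 direct resumption after events that Section 3.1.2.1 defines as DLTs, while Sections 3.1.2 and 4.6.2 require permanent discontinuation

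*Protocol*

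**What the plan says.** **The stopping rule.** Protocol Section 3.1.2 states: "Patients experiencing a DLT during the DLT window (first two cycles of treatment) will permanently discontinue study treatment". Section 4.6.2 lists the same trigger among its reasons for permanent discontinuation: "A DLT during the DLT window in patients enrolled in the dose-escalation phase". The same list has a separate trigger that is not limited to the DLT window: "Any adverse event that leads to a delay of more than 21 days in the start of the next treatment cycle". Section 4.6.2 then adds a proviso. When a toxicity is due to one drug only, the others may continue in a patient who is benefiting, after discussion with the Medical Monitor.

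**The DLT definition.** Section 3.1.2.1 covers events in the first two cycles that the investigator judges clearly unrelated to the lymphoma. One criterion is: "Adverse event of any grade that leads to a delay of more than 14 days in the start of the next treatment cycle". Others are prolonged Grade 4 neutropenia or thrombocytopenia, Grade 3 or 4 neutropenia with sustained fever or documented infection, and Grade 3 or 4 non-hematologic events outside a short list of exceptions.

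**The management tables.** Section 5.1.8 allows toxicity delays of up to 21 days in induction. For hematologic toxicity that improves to Grade 2 or less, Table 16 reads "or baseline 15–21 days after the scheduled date for the next cycle, resume obinutuzumab or rituximab at the full dose" and goes on to "resume the last escalated drug(s) at a reduced dose according to guidelines in Section 5.1.8.1 for current and subsequent cycles". For clinical or laboratory tumor lysis syndrome (TLS) of Grade 3 or less, Table 18 reads: "If symptoms (laboratory and clinical) have resolved completely, resume obinutuzumab or rituximab at full dose and resume venetoclax and idasanutlin at current dose". For Grade 3 diarrhea on Days 1 to 5, it tells sites to "withhold study treatment only if diarrhea does not improve to Grade" 2 or less within 48 hours, and to resume at a reduced dose after improvement.

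**The concern.** Section 5.1 sends sites to Section 5.1.8 for the criteria on dose modification, delay and discontinuation. Neither Section 5.1.8 nor Tables 16 to 18 excepts DLTs or refers back to Section 3.1.2 or 4.6.2. A site working from the tables would re-dose a patient whom Section 3.1.2 takes off treatment. A site working from Section 3.1.2 would stop that patient.

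The conflict falls where untested dose combinations are first given, so it is first a matter of patient safety. It also reaches the data. Exposure and later-cycle toxicity by dose level would depend on which page a site followed, and Section 3.1.2.2 allows toxicity after Cycle 2 to inform the MTD. If escalation patients treated at the RP2D are pooled with the expansion arm (Protocol Section 6.5, SAP Section 5), end-of-induction response would be affected too.

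**Working it through.** No model or power calculation applies. The check sets each DLT criterion beside the table instruction for the same event.

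**Do the tables reach escalation patients inside the DLT window?** Yes. Section 5.1.8 has rules for parallel and diagonal cohorts, which exist only in escalation. Table 16 refers to the drug or drugs last escalated. Table 17 applies only to Days 8 and 15 of Cycle 1, which for an escalation patient are always in the window. Its footnote b is written for the dose-escalation phase: it holds prophylactic G-CSF until after Cycle 2 but says nothing about DLTs.

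**Delay limits.** The DLT criterion is a delay of more than 14 days, so day 15 onward. Table 16 resumes at 15–21 days, and 21 − 15 + 1 = 7 days. All seven exceed 14, so the overlap is 7 of 7. At 14 days or fewer, this criterion is not met. Above 21 days, every rule stops treatment.

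**Events side by side (Cycles 1–2 of escalation, judged clearly unrelated to the lymphoma).**

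| Event | Section 3.1.2.1 | Management table |
|---|---|---|
| Hematologic recovery 15–21 days late | DLT | Table 16: resume, last escalated drug(s) reduced |
| First Grade 4 neutropenia (despite supportive care) or thrombocytopenia lasting over 7 days | DLT | Table 16: stop only if recurrent and after a dose reduction |
| First Grade 3–4 neutropenia with fever over 5 days or documented infection | DLT | Table 16: stop only if recurrent and after a dose reduction; Table 17: withhold, then resume |
| Grade 3 clinical TLS | DLT (only laboratory TLS without clinical signs is excepted) | Table 18: resume after resolution, oral drugs at current dose |
| Grade 3 AST/ALT increase lasting 7 days or more | DLT (under 7 days is excepted) | Table 18: withhold, then resume with venetoclax one level lower |
| Grade 3 diarrhea not controlled in 48 hours | DLT (response within 48 hours is excepted) | Table 18: withhold, then resume both oral drugs reduced |
| Other non-excepted Grade 3 non-hematologic events | DLT | Table 18: withhold, then resume both oral drugs reduced |

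**Where the texts agree.** Table 16 stops treatment for Grade 3 or 4 thrombocytopenia with Grade 3 or worse bleeding. Table 18 stops it for Grade 4 non-hematologic events and for Hy's Law cases. The conflict therefore covers many DLT criteria, but not all.

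**The case against.** The strongest defense is that the specific rule overrides the general one. Section 4.6.2 is a cumulative list that puts the DLT trigger beside the 21-day trigger, so the two limits can coexist: a patient stopped for a DLT never reaches a resume row. The tables are called guidelines, serve both phases and all six cycles, and do not repeat every stopping rule. Within the window they are still needed for non-DLT events, such as Grade 4 neutropenia of 7 days or less. Some patients in the 15–21-day row may have no DLT at all, for instance when a cytopenia is put down to marrow infiltration.

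Much of this stands. The 21-day maximum is not a contradiction by itself, and the override reading is plausible. But the protocol never states it. The authors adapted Table 17 to the dose-escalation phase for G-CSF and left DLTs unaddressed. The single-drug proviso in Section 4.6.2 also leaves unclear whether a DLT always ends all treatment.

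A reader might also infer that the DLT count feeding the modified Continual Reassessment Model (mCRM) will fall short. The documents do not show this. DLT status is set by Section 3.1.2.1 whatever is done with treatment, and Sections 3.1.2 and 5.4 require DLTs to be reported within 24 hours. Section 5.2.3 makes TLS of any grade, and Grade 3 or worse neutropenia and thrombocytopenia, immediately reportable. Under Section 3.1.2.2 the sponsor reviews the data after each cohort's window. A site could fail to label a manageable-looking event as a DLT, but that remains a possibility.

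**Conclusion.** The contradiction is in the text and should be reconciled. It is confined to Cycles 1 and 2 of dose escalation and to events the investigator judges clearly unrelated to the lymphoma. Within those limits it covers the seven kinds of event tabulated, including the whole of Table 16's 15–21-day band. The consequence is inconsistent re-dosing after a DLT, and so inconsistent exposure and later-cycle safety data.

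The effect on efficacy is conditional. Protocol Section 6 summarizes escalation data separately, and pooling of RP2D patients is optional.

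The number of patients affected cannot be derived. A reader might apply the 16%–33% target interval to the 60-patient maximum (0.16 × 60 = 9.6; 0.33 × 60 = 19.8) and speak of 10 to 20 patients. That would count every DLT if all 60 were treated at target-level doses, including the DLT types for which the texts agree. The documents give no split of DLTs by type.

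**What to change.** Add one statement to Section 5.1.8, repeated at the head of Tables 16, 17 and 18, saying which rule governs an event that meets Section 3.1.2.1 in the DLT window. It should say how the single-drug proviso in Section 4.6.2 applies to such an event. Align Sections 3.1.2 and 4.6.2 with it. Which clinical rule applies is for the sponsor to decide; the statistical need is that only one does.

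Optionally, confirm in the same place that the event is recorded as a DLT for the mCRM whatever is done with treatment. This restates what Sections 3.1.2.1 and 5.4 already imply.

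The cost is protocol wording: a sentence in Section 5.1.8, a line above three tables and matching text in two sections. It needs no extra patients or procedures.

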**Table 19 Guidelines for Management of Toxicities That Occur during Maintenance or Consolidation Treatment**

Event	Action to Be Taken
Hematologic toxicity: Grade 3 or 4	

• Withhold study treatment.

• Administer myeloid growth factors for neutropenia as allowed according to institutional guidelines.

• Administer RBCs or platelets as required.

• If improvement to Grade <math>\leq 2</math>, resume obinutuzumab or rituximab at full dose and resume venetoclax at next lower dose for subsequent cycles per guideline in Section 5.1.8. Patients who are not eligible for further venetoclax dose reductions should be permanently discontinued.

• If study treatment is withheld for <math>> 42</math> days, permanently discontinue study treatment.

• Withdraw venetoclax and idasanutlin in case of recurrent episodes of Grade <math>\geq 3</math> thrombocytopenia and/or neutropenia.

Non-hematologic toxicity: Grade $\geq 2$	

• Withhold study treatment.

• If improvement to Grade <math>\leq 1</math> or baseline, resume obinutuzumab or rituximab at full dose and resume venetoclax at the next lower dose for subsequent cycles per guideline in Section 5.1.8. Patients who are not eligible for further venetoclax and/or idasanutlin dose reductions should be permanently discontinued.

• If study treatment is withheld for <math>> 42</math> days, permanently discontinue study treatment.

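### Table 16 orders a dose reduction for recurrent Grade 3 cytopenia during induction but not for recurrent Grade 4, so in one branch the worse event gets the milder instruction

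*Protocol*

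**What the plan says.** Table 16 of the protocol (Section 5.1.8.1) has a single row that covers Grade 3 and Grade 4 hematologic toxicity together. Within it:

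- For patients with one prior dose reduction or none, treatment is withheld. If counts recover to Grade 2 or better, or to baseline, no later than 14 days after the next cycle was due, the site is to "resume obinutuzumab or rituximab at full dose and resume idasanutlin and venetoclax at current dose". Recovery at 15 to 21 days means a reduced dose; withholding beyond 21 days means discontinuation.
- Treatment stops permanently for "Grade 3 or 4 thrombocytopenia of any duration if associated with Grade" 3 or higher bleeding. It also stops for "Recurrent Grade 3 or 4 neutropenia if associated with fever of" more than 38°C for more than 5 days, or with a documented infection, but only after a prior reduction. The third criterion is "Recurrent Grade 4 neutropenia or thrombocytopenia lasting more than 7 days despite use of G-CSF (for neutropenia) and after one idasanutlin dose reduction", or after a venetoclax dose or schedule reduction.
- A separate block, "For patients who present with recurrent Grade 3 thrombocytopenia/neutropenia in consecutive cycles", orders both drugs reduced for later cycles if this happens despite G-CSF.

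Elsewhere, Table 19 (maintenance and consolidation) reads "Withdraw venetoclax and idasanutlin in case of recurrent episodes of Grade" 3 or higher thrombocytopenia or neutropenia, so it includes Grade 4. Section 4.6.2 lists as a stopping reason "Any hematologic adverse event that meets criteria for permanent discontinuation according to the guidelines provided in Section 5.1.8". Section 3.1.2 adds, for dose escalation, "Patients experiencing a DLT during the DLT window (first two cycles of treatment) will permanently discontinue study treatment".

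**The concern.** The recurrence block is the only text in Table 16 that orders a reduction because a cytopenia has come back, and it names Grade 3 alone. A recurrent Grade 4 event with timely recovery is left to the general rule, which makes no distinction between a first and a repeated event and returns the patient to the current dose. The more severe toxicity then gets the milder instruction.

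There is a knock-on effect. The stopping rule for Grade 4 lasting more than 7 days applies only after a reduction. If Table 16 never orders one because recovery always falls within 14 days, the patient may never become eligible for that rule.

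The stake is patient safety and dose received. Section 5.1.8 bars re-escalation, so whether a reduction is made at the recurrence sets the dose for the induction cycles that remain. Sections 5.1.5.1 and 5.1.5.2 anticipate severe overlapping thrombocytopenia and neutropenia with this triplet, so the branch is foreseeable.

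**Working it through.** The protocol gives no figure to reproduce here. The check is a trace of the rules, followed by a simple dose calculation.

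**Conditions for the branch.** One prior reduction or none; outside Cycles 1 and 2 of dose escalation; cytopenia in consecutive cycles despite G-CSF; still present on the scheduled next-cycle date; recovered to Grade 2 or better, or baseline, within 14 days after that date; no Grade 3 or higher bleeding; no qualifying fever or infection after a prior reduction.

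**Trace.**

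| Recurrent event | Table 16 result |
|---|---|
| Grade 3 | Recurrence block applies: reduce idasanutlin; reduce venetoclax dose or schedule |
| Grade 4, 7 days or less | No stopping rule met, not named in the recurrence block: current dose |
| Grade 4, more than 7 days, no prior reduction | Stopping rule needs a prior reduction, so not met: current dose |
| Grade 4, more than 7 days, after a reduction | Permanent discontinuation |

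The first line takes the recurrence block, as the more specific text, to prevail over the general 14-day rule.

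**Does another provision close the gap?**

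- Section 4.6.2 sends hematologic events back to Section 5.1.8, and its 21-day delay limit is not reached.
- The Grade 4 stop in Table 18 belongs to the non-hematologic table.
- The DLT rule applies only to Cycles 1 and 2 of dose escalation. It does not reach later cycles or the expansion phase of about 80 patients.

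**Why the persistence condition matters.** Section 5.1.8 says toxicities that subside before the next cycle should not trigger the modifications. If counts recover before the due date, neither grade leads to a reduction and there is no contrast.

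**Illustrative size.** Expansion patient, cytopenia outlasting the due date after Cycles 2 and 3, with the reduction taking effect from Cycle 4. The Step 1 reductions are from Table 15; cut = reduction / initial dose.

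- Six-cycle idasanutlin (Regimen A, DLBCL): Cycles 1 to 3 full, Cycles 4 to 6 reduced; share = (3 + 3(1 − cut)) / 6.
- Regimen B (idasanutlin in Cycles 2 to 6): Cycles 2 and 3 full, Cycles 4 to 6 reduced; share = (2 + 3(1 − cut)) / 5.

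| Initial dose (mg) | After Step 1 (mg) | Cut | Six cycles | Regimen B |
|---|---|---|---|---|
| 100 | 50 | 50.0% | 75.0% | 70.0% |
| 150 | 100 | 33.3% | 83.3% | 80.0% |
| 200 | 150 | 25.0% | 87.5% | 85.0% |
| 250 | 150 | 40.0% | 80.0% | 76.0% |
| 300 | 200 | 33.3% | 83.3% | 80.0% |
| 350 | 250 | 28.6% | 85.7% | 82.9% |
| 400 | 300 | 25.0% | 87.5% | 85.0% |

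Example at 100 mg: (3 + 3 × 0.5) / 6 = 75.0%; (2 + 3 × 0.5) / 5 = 70.0%. Recurrent Grade 4 as written: no cut, so 100% in both.

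**The case against.** The best answer is that this is an obvious slip. The block sits in a row that covers both grades. The stopping rule for recurrent Grade 4 presupposes that such patients have been reduced, and Table 19 uses Grade 3 or higher. Section 5.1.8 says the doses may be reduced and allows dosing only if the clinical and laboratory assessment is acceptable. Table 16 is a guideline, and Grade 3 or higher neutropenia and thrombocytopenia are reported to the sponsor within 24 hours. An experienced investigator would probably reduce anyway.

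Much of this stands as evidence of intent, and it makes the point one of wording, not of design. It does not cure the text. The same table cell writes Grade 3, Grade 3 or 4, and Grade 4 as separate triggers, so Grade 3 cannot safely be read as Grade 3 or higher. For timely recovery the cell expressly says current dose.

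Three stronger readings are tempting but not supported:

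- *That every recurrent Grade 4 patient stays on full dose.* Recovery after 14 days, bleeding, the criteria that follow a prior reduction, and DLTs all lead elsewhere. With exactly two prior reductions Table 16 gives no resumption rule at all.
- *That a Grade 3 patient at venetoclax 200 mg must be discontinued, which would void the contrast.* Section 5.1.8 bars reduction below 200 mg, but the recurrence block also allows a shorter venetoclax schedule.
- *That the diarrhea row of Table 18 is a second defect, since it reduces doses after in-cycle Grade 3 diarrhea despite the Section 5.1.8 exemption.* The footnote printed under the diarrhea rows omits the exemption sentence; the version containing it sits under other rows. The row also treats in-cycle diarrhea separately from diarrhea present at the next planned cycle, and orders the reduction for the current cycle as well. It plainly operates as a specific rule over the general one.

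**Conclusion.** The point holds in a limited form. As written, Table 16 tells a site to reduce for recurrent Grade 3 cytopenia and to resume at the current dose for recurrent Grade 4, under the conditions listed in the check.

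In the illustration this means 75.0% to 87.5% of planned induction idasanutlin for Grade 3 (70.0% to 85.0% under Regimen B) against 100% for Grade 4. The figures rest on persistence past the due date after both Cycles 2 and 3, and on one Table 15 step being taken. They cover initial doses of 100 to 400 mg only: Table 15 stops there, although Section 3.1.2.3 allows idasanutlin up to 600 mg. The low ends arise solely at 100 mg, and the expansion dose is not yet fixed. The documents give no rate of recurrent Grade 4 cytopenia for this triplet, so the number of patients affected cannot be estimated.

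A reader might infer that recommended-dose selection or the primary response analysis is compromised. Nothing in the documents shows that. The point is worth correcting because the instruction runs the wrong way on a safety matter and the correction is cheap.

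**What to change.** In the recurrence block of Table 16, insert the words *or 4* after Grade 3, so that it covers recurrent Grade 3 or 4 thrombocytopenia or neutropenia in consecutive cycles despite G-CSF. Leave the permanent discontinuation criteria as they are. A Grade 4 patient reduced under the amended block can then also meet the criterion for Grade 4 lasting more than 7 days if the event recurs.

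The cost is a two-word edit at the next amendment, with no change to design, sample size, data collection or analysis.
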